## 6.2. Summary of Study Design

Study I5F-MC-JSCB (JSCB) is a single-center, open-label, nonrandomized, noncontrolled Phase 1 study of I.V. LY3022855 in patients with advanced, refractory breast or prostate cancer. Eligible patients will receive LY3022855 as an infusion, suggested to be administered over approximately 90 minutes for the first infusion, decreasing by 30 minutes for subsequent infusions, until administered over 30 minutes (refer to Section [7.2](#) for further details of study drug administration). Study JSCB is intended to explore clinical response and immunological activity of single-agent LY3022855 in approximately 40 patients (enrolled, of whom 36 will be evaluable), by assessment of biomarkers, cytokines, and immune cells. The study schema is shown in [Figure JSCB.3](#).

### Patients with prostate cancer

### Patients with breast cancer

\*Additional patients may be enrolled if marked antitumor activity is demonstrated at this dose.

Abbreviations: LY = LY3022855 (IMC-CS4); PD = progressive disease.

### Figure JSCB.3. Study JSCB study design.

Enrollment will be sequential, starting with the assignment of patients to Dosage A (LY3022855, 1.25 mg/kg every 2 weeks [Q2W] of a 6-week cycle), then the assignment of patients to Dosage B (LY3022855, 1.0 mg/kg on Weeks 1, 2, 4, and 5 of a 6-week cycle) once the Dosage A cohort is fully enrolled. Once the Dosage B breast cancer cohort is fully enrolled, patients with breast cancer will be assigned by the sponsor to Dosage C (LY3022855, 100 mg QW of a 6-week cycle) or D (LY3022855, 100 mg Q2W of a 6-week cycle) on an alternating basis until 5 patients are enrolled to each of Dosages C and D. Once 5 patients are enrolled to each of Dosages C and D, the sponsor and the investigators will review clinical data to determine if enrollment of an additional 5 patients to each of Dosages C and D is warranted (refer to Section 10 for details regarding sample size).

Patients will receive Dosage A, B, C, or D for one 6-week cycle or until the patient meets one or more criteria for study discontinuation. After 1 cycle, patients who are benefitting from study treatment (that is, no disease progression or unacceptable toxicity) may continue to receive study treatment at the same dose and schedule until there is clear (confirmed) evidence of disease progression or other withdrawal criteria are met. At the time of study completion, if a patient continues to benefit from study treatment, that patient may enter the continued access period.

Immune studies will include evaluations of changes in baseline over time in: (1) peripheral blood immune cell subsets, as determined by flow cytometric analysis using an antibody panel, and that may include but not be limited to the following markers: Live-Dead, CD3, CD4, CD8, CD14, CD16, FoxP3, PD-1, Ki-67, CTLA-4, TIM-3, LAG-3, and ICOS, as well as (2) serum cytokines, as determined by MSD multiplex cytokine immunoassay technology or ELISA, and that may include but not be limited to CSF-1, IFN- $\gamma$ , IL-1 $\beta$ , IL-2, IL-4, IL-6, IL-8, IL-10, IL-12p70, IL-13, IL-34, and TNF- $\alpha$ . Blood samples for the immunomodulatory studies will be taken as described in [Attachment 4](#), [Attachment 5](#), and [Attachment 6](#).

In addition, for all patients, 2 separate tumor biopsy procedures will be performed (attempted): the first will be performed at baseline (predose), within 14 days prior to dosing on Cycle 1, Day 1, and the second will be performed within 14 days prior to dosing on Cycle 2, Day 1. Biopsy samples will be flash frozen, for exploratory biomarker research, to be used in understanding the pharmacodynamic effects of LY3022855. To ensure adequate enrollment for the immune studies, additional patients will be enrolled as needed to replace a patient who either: (1) discontinues from the study prior to the second biopsy procedure, or (2) does not have sufficient tumor tissue for the second biopsy procedure and in the opinion of the investigator is benefitting from study treatment (in which case, the patient will be allowed to remain on study treatment). In addition to the required blood and tumor samples previously noted, optional tumor biopsies and/or blood samples for biomarker research may be obtained at the investigator's discretion in discussion with the patient, such as at the time of radiographic response or treatment progression.

For patients with measurable disease per RECIST, clinical endpoints for response will be standard tumor response as determined by RECIST 1.1 and irRECIST criteria. For the prostate cancer cohort only, progression in bone will be determined by using the PCWG2 criteria, which defines progression as the point at which at least 2 new lesions are observed on bone scan (compared with baseline), and are then confirmed on a follow-up bone scan performed at least 6 weeks later. However, if the point when the new lesions are observed is the first interval bone scan (that is, Week 6), then the confirmatory bone scan must demonstrate at least 2 additional new lesions (that is, a total of at least 4 new lesions from baseline). Further details of the PCWG2 criteria are provided in Section [8.3](#).

To document the immunomodulatory activity of LY3022855 treatment in patients with advanced, refractory breast or prostate cancers, an adequate sample size is required (refer to Section 10).

The planned duration of treatment is not fixed; patients will remain on study until they fulfill one of the criteria for study discontinuation (Section 6.3).

Refer to [Attachment 1](#) for the Study Schedule.

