## **7.3. Method of Assignment to Treatment**

Patients who meet all criteria for enrollment will be assigned to receive LY3022855 in this study. Before each patient's enrollment into the study, an eligibility check must be conducted between the investigational site and the Lilly clinical research personnel to confirm that each patient meets all enrollment criteria. Upon confirmation of eligibility, the sponsor will confirm the dose and identification number assignment for each patient.

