## **7.4. Blinding**

This is an open-label study.

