## 10.6. Pharmacodynamic Analyses

Pharmacodynamic data from all patients undergoing pharmacodynamic assessments will be analyzed.

To study the impact of the study drug and the dose levels on the patients, the changes from baseline over time in peripheral blood immune cell subsets will be documented. The immunomodulatory activity of LY3022855 will be documented by examining markers that include, but are not limited to: Live-Dead, CD3, CD4, CD8, CD14, CD16, FoxP3, PD-1, Ki-67, CTLA-4, TIM-3, LAG-3, and ICOS. The expression of those markers will be quantified by flow cytometric analysis with an antibody panel.

In addition, changes from baseline over time in serum cytokines will be determined by MSD multiplex cytokine immunoassay or ELISA. The markers to be measured using these technologies include, but are not limited to: CSF-1, IFN- $\gamma$ , IL-1 $\beta$ , IL-2, IL-4, IL-6, IL-8, IL-10, IL-12p70, IL-13, IL-34, and TNF- $\alpha$ .

Biomarker measures of protein expression, based on flow cytometry, MSD, and ELISA, will be summarized by tumor type and/or dosage, based on enrolled patients. Summary statistics may include means, medians, corresponding standard errors, quartiles, and ranges. Graphics, including profile plots of markers over time, will be generated to explore potential patterns between patients. Correlation analyses between biomarkers and relative laboratory tests may be performed to further explore the activity of LY3022855.

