6.1. General Considerations

Statistical analysis of this study will be the responsibility of the sponsor. The analyses for this study will be descriptive, except for exploratory analyses of biomarker data, as deemed appropriate. Analyses of the biomarker data will be described in a separate biomarker SAP.

Data analyses will be provided by cancer type, dose group, and for all study patients combined, wherever appropriate. For continuous variables, summary statistics will include number of patients, mean, median, standard deviation, minimum, and maximum. Categorical endpoints will be summarized using number of patients, frequency, and percentages.

The following data handling conventions will be used in the analysis (see [Table 6.1](#)).

Table 6.1. Data Handling Conventions

Term	Definition or Rule
Relative Study Day	If assessment is on or after date of first dose then (date of assessment) – (date of first study drug dose) +1
	If assessment precedes first dose of drug then (date of assessment) – (date of first study drug dose)
	There is no study day 0. Study day 1 is the date of first dose and study day -1 is the day before the first dose.
Baseline	For change from baseline analyses, baseline value is defined as the last reported measure on or before the first dose date (prior to the dose administration), unless, otherwise, specified. For change from baseline within a cycle, baseline value is defined as the measure prior to the first dose of that cycle, unless, otherwise, specified.
Entered	Patients who have signed the informed consent document directly.
Enrolled population	Patients who have been assigned to study treatment and have received at least 1 dose of any study treatment.
Screen Failures	Patients who have signed informed consent, do not meet eligibility criteria and are not enrolled.
Evaluable population	Patients who complete 1 cycle of LY3022855 treatment, undergo 1 baseline and 1 posttreatment tumor biopsy procedure, and complete immune blood studies for 1 cycle
Safety Population	Patients who have received at least 1 dose of study drug.

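### Alternating between Dosages C and D at one open-label site makes at least 9 of the first 10 assignments foreseeable; a concealed sponsor-held list would reduce this at little cost

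*Protocol*

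**What the plan says.** Protocol Section 6.2 describes a "single-center, open-label, nonrandomized, noncontrolled Phase 1 study of I.V. LY3022855", and Section 7.4 confirms the absence of blinding: "This is an open-label study". Dosages A and B are filled in sequence. Once the Dosage B breast cohort is full, "patients with breast cancer will be assigned by the sponsor to Dosage C" or to Dosage D, "on an alternating basis until 5 patients are enrolled to each of Dosages C and D". The starting dosage is not given.

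Section 7.3 places a central step before treatment. First, "an eligibility check must be conducted between the investigational site and the Lilly clinical research personnel"; then "the sponsor will confirm the dose and identification number assignment for each patient". No random list or concealment is described.

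For stage 2, Section 6.2 refers to five more patients on each of C and D, and Section 10 to five more on whichever dosage passes. Neither says how patients are assigned if both are open. Sections 6.2 and 7.6.1 provide for replacing nonevaluable patients, without an assignment rule.

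On analysis, Protocol Section 10.6 introduces the marker summaries with the aim "To study the impact of the study drug and the dose levels on the patients". SAP Section 6.1 states: "Data analyses will be provided by cancer type, dose group, and for all study patients combined". The same SAP section calls the analyses descriptive apart from exploratory biomarker work.

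**The concern.** Staff who propose patients at a single open-label site know every past assignment. Under alternation they also know the next one before they put a patient forward. The eligibility check confirms that a patient qualifies; it does not control when, or in what order, qualifying patients are presented.

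There is room for selection. Section 6.1.1 admits ECOG status 0 to 2, relies on investigator-judged life expectancy, and allows ongoing antiestrogen or trastuzumab therapy in some patients. Section 5.5 gives a reason to favor each dosage: stronger target engagement with weekly dosing, and antitumor activity seen so far only on the every-2-week schedule. With five patients per dosage in stage 1, one or two placed by choice can change a group's profile.

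Within breast cancer, C and D are the only dosages recruited at the same time, so this is the one dosage contrast free of calendar-time differences. Readers will compare the two columns even without a test. What is at stake is whether a visible difference in markers, safety or response can be attributed to the dosage rather than to who was put forward for it.

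**Working it through.** **Inputs.** Stage 1 is 5 + 5 patients at 1:1 (Protocol Sections 6.2 and 10); one site, open-label (Sections 6.2 and 7.4). Per dosage: at least 2 of 5 responders to continue, at least 5 of 10 to succeed, 20% versus 60% response, one-sided 5%, 80% power (Section 10; SAP Section 5.2).

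**Step 1: the plan's own figure.** Power = sum over x = 2 to 5 of P(X1 = x) × P(X2 ≥ 5 − x), where X1 and X2 are Binomial(5, p).

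- p = 0.6: 0.2304 × 0.68256 + 0.3456 × 0.91296 + 0.2592 × 0.98976 + 0.07776 × 1 = 0.807.
- p = 0.2: 0.2048 × 0.05792 + 0.0512 × 0.26272 + 0.0064 × 0.67232 + 0.00032 × 1 = 0.030.

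The stated 80% power and 5% limit are reproduced. Neither calculation involves the method of assignment, so changing that method leaves both as they are.

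**Step 2: alternation.** Assume strict one-by-one alternation. After the first patient, 9 of 10 assignments are fixed. Expected correct guesses are 9 + 0.5 = 9.5, or 10 if the starting dosage is known.

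**Step 3: a random list with a forced 5:5 split.** Assume the site knows all past assignments and the split, and always guesses the dosage with more places left. For one block of 2m:

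- expected correct guesses = m + (2^(2m) / C(2m, m) − 1) / 2
- expected fully determined assignments = 2m / (m + 1)

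With m = 5: 5 + (1024/252 − 1)/2 = 6.53 guesses, and 10/6 = 1.67 determined, or 16.7% of 10. The same formulas give the smaller blocks.

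| First 10 patients | Correct guesses | Fully determined |
|---|---|---|
| Alternation | 9.5 to 10 | 90% to 100% |
| Blocks of 2 | 7.5 | 50% |
| Blocks 4 + 4 + 2 | 7.17 | 36.7% |
| One 5:5 block of 10 | 6.53 | 16.7% |
| Simple 1:1 randomization | 5 | 0% |

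Simple randomization removes predictability but gives exactly 5:5 only 252/1024 = 24.6% of the time. Small blocks give back much of the gain.

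**Step 4: visit burden in Cycle 1.** Combining Protocol Attachment 1 (weekly laboratory tests on all schedules) with Attachments 5 and 6 (sampling), Dosage C has Days 1, 2, 8, 15, 22, 29 and 36 (seven). Dosage D has Days 1, 2, 8, 15, 22, 29, 30 and 36 (eight).

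**The case against.** The design is declared nonrandomized, and alternation is consistent with that label, so the plan does not contradict itself. That stands, and it makes this a question of design choice. The label does not, however, make alternation as good as a concealed list.

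A reader might infer that selection between C and D would distort the expansion decision. The documents do not support this. Section 10 judges each dosage alone, by its responder count against a fixed 20% rate. No C-versus-D test or selection rule exists, and randomizing between the two would not correct the choice of fitter patients for both.

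A reader might also take the fewer visits mentioned for Dosage D in Section 5.5 as a ready motive for steering. In Cycle 1 that motive is absent: eight scheduled days for D against seven for C. The other reasons in Section 5.5 remain.

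Finally, the figures above measure guessing, not bias, and chance is large at this size. If, for illustration, 4 of 10 patients were fitter, a random 5:5 split would divide them 3:1 or 4:0 in 1 − 120/252 = 52% of lists. The exact 95% interval for 2 of 5 responders is about 5% to 85%. Randomization would not make a 5-versus-5 contrast precise. It would make such imbalance less open to choice, which is the limited gain claimed.

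**Conclusion.** The point holds as an optional improvement. At least 9 of the first 10 C/D assignments are foreseeable, 10 of 10 if the starting dosage is known. A concealed 5:5 list would bring fully determined assignments down to about 17% and best-strategy correct guesses to about 6.5 of 10.

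Two stronger readings go too far. One is that every allocation in C and D is predictable: alternation is specified only for the first 5 + 5, stage 2 has no stated method, and if only one dosage expands there is nothing to allocate. The other is that a random list removes the problem: with a forced 5:5 split and known history, some assignments stay guessable.

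The result assumes strict alternation, site knowledge of all past assignments, and no replacement entering out of sequence. The documents do not show that steering would occur, and no size of bias in any marker or response estimate can be derived from them. The benefit is confined to the descriptive summaries by dosage.

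**What to change.** In Protocol Section 6.2, replace alternation with assignment from a concealed, computer-generated 1:1 list held by the sponsor, giving 5:5 over the first 10 patients. Release each assignment only after the Section 7.3 eligibility check is complete. Keep the block structure out of the protocol, and avoid small blocks.

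Extend the list to cover replacements of nonevaluable patients. Use it in stage 2 whenever both dosages are open at the same time; because the interim reviews are done per dosage, the two may open at different times, and the text should say that a dosage open alone needs no allocation.

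Amend the nonrandomized description for the C/D assignment in the Protocol Synopsis, Protocol Section 6.2 and SAP Section 5.1. The study report should still present C versus D as descriptive.

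The cost is one list and these wording changes. The sponsor's dose-confirmation step already exists. No patients, visits or procedures are added, and the planned 10 per dosage, power (0.807) and per-dosage type I error (0.030) are unchanged.

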### **6.2.1. Study Completion and End of Trial**

This study will be considered complete (that is, the scientific evaluation will be complete [study completion]) when 36 evaluable patients\* are attained. “End of trial” refers to the date of the last visit or last scheduled procedure for the last patient.

\* Patients are considered evaluable if they complete 1 cycle of treatment (at least Cycle 1, Day 43, based on a 6-week cycle), undergo 1 baseline and 1 posttreatment tumor biopsy procedure (ie, attempted, whether the biopsy is successful or not), and complete immune blood studies for 1 cycle.

### **6.2.2. Continued Access Period**

All patients remaining on study treatment without disease progression following the final analysis of the primary and secondary endpoints will be able to enter the continued access period of the study. The continued access period begins after study completion and ends at the end of trial. During the continued access period, patients on study treatment who continue to experience clinical benefit may continue to receive study treatment until disease progression, death, unacceptable toxicity, or start of new anticancer treatment. The continued access period includes a follow-up visit. The follow-up visit begins after the last dose of study drug and lasts approximately 30 days. If it is deemed to be in the best interest of the patient to start a new anticancer treatment prior to the scheduled end of the follow-up visit, the follow-up visit duration may be shortened. In this case, the follow-up assessments should be completed prior to the initiation of the new therapy.

Lilly will notify investigators when the continued access period begins.

During the continued access period, all AEs, SAEs, study drug dosing, and dose reduction of treatment will be collected on the electronic case report form (eCRF).

Serious adverse events will also be reported to Lilly Global Patient Safety and collected in the pharmacovigilance system. In the event that an SAE occurs, additional information (such as local laboratory results, concomitant medications, and hospitalizations) may be requested by Lilly in order to evaluate the reported SAE.

Investigators may perform other standard procedures and tests needed to treat and evaluate patients; however, Lilly will not routinely collect the results of these assessments.

## 6.3. Discontinuations

### 6.3.1. Discontinuation of Patients

The criteria for enrollment must be followed explicitly. If the investigator site identifies a patient who did not meet enrollment criteria and who was inadvertently enrolled, the sponsor must be notified. If the sponsor identifies a patient who did not meet enrollment criteria and who was inadvertently enrolled, the investigator site will be notified. A discussion must occur between the sponsor clinical research physician (CRP) and the investigator to determine whether the patient may continue in the study, with or without investigational product. Inadvertently enrolled patients may be maintained in the study and on investigational product when the Lilly CRP agrees with the investigator that it is medically appropriate for that patient. The patient may not continue in the study with or without investigational product if the Lilly CRP does not agree with the investigator's determination that it is medically appropriate for the patient to continue. The investigator must obtain documented approval from the Lilly CRP to allow the inadvertently enrolled patient to continue in the study with or without investigational product.

In addition, patients will be discontinued from the study drug in the following circumstances:

- Enrollment in any other clinical trial involving an investigational product or enrollment in any other type of medical research judged not to be scientifically or medically compatible with this study.
- Investigator/Physician Decision
  - the investigator/physician decides that the patient should be discontinued from the study or study drug(s)
  - if the patient, for any reason, requires treatment with another therapeutic agent that has been demonstrated to be effective for treatment of the study indication, discontinuation from the study drug(s) occurs prior to introduction of the other agent
- Patient Decision
  - the patient or the patient's designee (for example, parents or legal guardian) requests to be discontinued from the study or study drug
- Sponsor Decision
  - Lilly stops the study or stops the patient's participation in the study for medical, safety, regulatory, or other reasons consistent with applicable laws, regulations, and GCP

- The patient has confirmed evidence of progressive disease.
  - Exceptions for continuing with study treatment beyond confirmed radiographic progression may be made on a case-by-case basis for patients who are believed to be clinically benefiting from protocol therapy and both the investigator and sponsor (the CRP/clinical research scientist [CRS]) agree that continuing protocol therapy is in the patient's best interest.
- The patient experiences unacceptable toxicity.
- The patient experiences a Grade 3 or 4 infusion-related reaction (IRR) to LY3022855.
- The patient experiences Grade  $\geq 2$  AST or ALT elevation and Grade  $\geq 2$  bilirubin elevation (cases confirmed by Hy's Law).
- The patient is noncompliant with study procedures and/or treatment (Section 7.6).

The reason for and date of discontinuation will be collected for all patients. The Date of Discontinuation (for any of the above reasons) from study treatment is to be reported on the eCRF. Patients who discontinue will have follow-up procedures performed as shown in the Study Schedule ([Attachment 1](#)).

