#### **8.1.4. Safety Monitoring**

The Lilly CRP or CRS will monitor safety data throughout the course of the study.

Representatives from Lilly Global Patient Safety will specifically monitor SAEs. Lilly will review SAEs within time frames mandated by company standard operating procedures. The Lilly CRP/CRS will, as is appropriate, consult with the functionally independent Global Patient Safety therapeutic area physician or clinical research scientist, and periodically review:

- Trends in safety data.
- Laboratory analytes, including AP, ALT, AST, CK, LDH, and C-reactive protein.
- Adverse events, including monitoring of hepatotoxicity and muscle damage.
- If a study patient experiences elevated ALT  $\geq 5 \times$  ULN and elevated total bilirubin  $\geq 2 \times$  ULN, clinical and laboratory monitoring should be initiated by the investigator.
- For patients entering the study with ALT  $\geq 3 \times$  ULN, monitoring should be triggered at ALT  $\geq 2 \times$  baseline.

Details for hepatic monitoring depend upon the severity and persistence of observed laboratory test abnormalities. To ensure patient safety and to comply with regulatory guidance, the investigator is to consult with the Lilly CRP/CRS regarding collection of specific recommended clinical information and follow-up laboratory tests (see [Attachment 3](#)).

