			AST or ALT $>5 \times$ ULN  AND  total bilirubin $>$ ULN	Withhold drug. Administer steroids (1-2 mg/kg/d prednisone). Consider resuming protocol treatment once total bilirubin $\leq$ ULN.  Discontinue protocol therapy permanently if bilirubin does not return to below the ULN within 3 wk of holding drug.
		3 or 4	GGT or alkaline phosphatase	Continue protocol treatment provided patient remains without other evidence of liver toxicity.
Musculoskeletal	Muscle abnormality		CK $>2.5 \times$ but $\leq 10$ ULN  AND  Serum and urine myoglobin $\leq$ ULN	Discuss with sponsor and consider continuing protocol treatment provided patient remains without other evidence of muscle or renal toxicity.
			CK $\geq 2.5 \times$ ULN  AND  Serum and urine myoglobin $>$ ULN	Withhold drug. Administer steroids (1-2 mg/kg/d prednisone). Consider resuming protocol treatment once serum and urine myoglobin $\leq$ ULN.  Discontinue protocol therapy permanently if serum and urine myoglobin does not return to below the ULN within 3 wk of holding drug.

System Organ Class	Adverse Event	CTCAE, Version 4.0 Grade (if applicable) and/or Symptoms a		Treatment Plan b
		Grade	Symptoms	
Nervous	Weakness, paresthesia (for example, Guillain-Barré syndrome, myasthenia gravis)		No impact on activities of daily living (ADL)	Withhold drug. Resume drug when symptoms resolve.
			Impact on ADL	Withhold drug. Administer appropriate medical intervention and steroids (1-2 mg/kg/d prednisone). Can resume drug during taper and after discussion with sponsor.
Respiratory	Dyspnea, hypoxia, pneumonitis	1		Consider to withhold drug. Resume drug when stable.
		2	Mild to moderate symptoms	Withhold drug. Administer steroids (1-2 mg/kg/d prednisone). Can resume drug during taper.
		≥3	Severe	Permanently discontinue drug. Administer steroids (1-2 mg/kg/d prednisone).  If >2 days despite steroids, add nonsteroid immunosuppressive.
Renal and urinary	Elevated creatinine, decreased urine output, blood in urine, edema	1	<1.5 × baseline	Continue drug.
		2 to 3	>1.5 × ULN but <6 × ULN	Withhold drug. Administer steroids (1- 2 mg/kg/d prednisone). If symptoms resolve to Grade ≤1, taper steroids over 1 month. Can resume drug during taper.
			OR  >1.5 × baseline	If elevations persist >7 days or worsen treat with Grade 4 recommendations.
		4	>6 × ULN	Permanently discontinue drug. Administer steroids (1-2 mg/kg/d prednisone).

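### Section 6.3.1 stops study drug for combined liver elevations after which the Attachment 10 hepatobiliary row allows resumption, and that row does not defer to Section 6.3.1

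*Protocol*

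**What the plan says.** Section 6.3.1 introduces its list in mandatory terms: "patients will be discontinued from the study drug in the following circumstances". One entry is AST or ALT at Grade 2 or above together with Grade 2 or above "bilirubin elevation (cases confirmed by Hy's Law". No route back to treatment is given. Events are graded by CTCAE v4.0, but the protocol prints no numeric Grade 2 cut-points and does not define Hy's Law.

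Attachment 10 has a hepatobiliary row for "AST or ALT $>5 \times$ ULN AND total bilirubin $>$ ULN". Its plan is to withhold drug and give steroids, then: "Consider resuming protocol treatment once total bilirubin $\leq$ ULN". The stop becomes permanent on one condition: "Discontinue protocol therapy permanently if bilirubin does not return to below the ULN within 3 wk of holding drug".

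Section 8.1.4 has two hepatic triggers. The main one is ALT of at least 5×ULN with "elevated total bilirubin $\geq 2 \times$ ULN, clinical and laboratory monitoring should be initiated by the investigator"; AST is not named. The second applies to patients entering with ALT of at least 3×ULN and fires at twice their baseline ALT, with no bilirubin condition.

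On status, Section 7.2.1.2.1 describes Attachment 10 as a guideline for suspected immune-related events that local standards may override. Sections 6.2 and 7.2.1 make continued treatment depend on no withdrawal criterion being met.

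**The concern.** A stopping rule and a management table cover some of the same laboratory results and end differently: one in discontinuation, the other in a possible return to treatment. A reader working from the Attachment 10 row sees nothing to say that Section 6.3.1 may already have settled the matter. At stake is consistent application of a safety stopping rule and, where the two readings diverge, the recorded reason for discontinuation. Separately, the trigger for hepatic monitoring in Section 8.1.4 has a higher bilirubin limit than the row that withholds drug.

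**Working it through.** No sample size or power figure is involved. The check sets the rules side by side as conditions. Let A be AST or ALT and B total bilirubin, both in multiples of ULN.

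**Inputs**
- Attachment 10 row: A > 5 and B > 1, with no upper limit on either.
- Section 6.3.1: A > a and B > b, where a and b are the Grade 2 cut-points. The documents do not print them, so they are varied as an assumption.
- Section 8.1.4, main trigger: ALT ≥ 5 and B ≥ 2.
- Section 8.1.4, second trigger: entry ALT ≥ 3 and current ALT ≥ 2 × entry ALT.

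**Section 6.3.1 against Attachment 10.** Both apply when A > max(5, a) and B > max(1, b). Because the row is unbounded above, this region is non-empty for any finite cut-points. With a taken as 2, 3, 5 or 8 and b as 1, 1.5, 2 or 3 (4 × 4 = 16 pairs), the overlap is present in all 16. The narrowest case, a = 8 and b = 3, still leaves every result with A > 8 and B > 3. Restricting Section 6.3.1 to confirmed Hy's Law cases shrinks the region. It does not empty it, provided the definition admits some cases with A > 5 and B > 1, because the row does not exclude confirmed cases. In the overlap, Section 6.3.1 discontinues; Attachment 10 withholds and lets resumption be considered once B ≤ 1.

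**Section 8.1.4 against Attachment 10.** The withhold row is met and the main trigger is not when ALT > 5 and 1 < B < 2. Take ALT 6 and B 1.5: 6 > 5 and 1.5 > 1, so drug is withheld; 6 ≥ 5 but 1.5 < 2, so the main trigger is not met. The second trigger then depends on entry ALT:
- Entry ALT below 3: the second trigger does not apply, so neither is met.
- Entry ALT 3: 2 × 3 = 6, and 6 ≥ 6, so monitoring is triggered.
- Entry ALT 5 (the eligibility ceiling with liver involvement, Section 6.1.1): 2 × 5 = 10, and 6 < 10, so it is not triggered.

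The ALT limits are practically equal (above 5 against at least 5, differing only at exactly 5). The mismatch lies in the bilirubin limit (above 1 against at least 2) and in AST, which can meet the withhold row alone but is absent from Section 8.1.4.

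**Hold limits.** Attachment 10 counts 3 weeks from holding drug, to bilirubin below ULN, for this row. Section 7.2.1 counts 4 weeks from the last dose given, to baseline or below Grade 2, for the Table JSCB.3 toxicities. Start point, target and scope all differ, and a shorter row-specific limit can sit inside a general maximum.

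**The case against.** The strongest reply is that precedence is already there in substance. Section 6.3.1 is mandatory, Attachment 10 only invites consideration and may be overridden, and Sections 6.2 and 7.2.1 allow continuation only while no withdrawal criterion is met. On that reading, meeting Section 6.3.1 removes the option in Attachment 10. This softens the conflict considerably. It does not close it: those sections govern continuation and dose reduction in the main text, and neither Section 7.2.1.2.1 nor the Attachment 10 row mentions Section 6.3.1.

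The Hy's Law qualifier also narrows the stopping rule. That stands, but by how much cannot be known while the term is undefined.

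A reader might infer from the monitoring mismatch that patients go unobserved. The documents do not support that. Chemistry is weekly for the first 12 weeks (Attachment 1), Section 7.2.1.2 asks for close watch on transaminases and bilirubin, Attachment 3 allows hepatic tests for a treatment-emergent abnormality, and Attachment 10 calls for a work-up whenever its plan is used. A monitoring trigger and a withholding trigger also need not be identical.

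A reader might also infer that, because transaminase rises are expected with this drug, the conflict will arise often and shift evaluability. That does not follow. Section 5.4.4.2 reports transaminase rises in monkeys without bilirubin change, and Section 5.4.5 discusses CK and AST rises without other laboratory signs of end-organ damage. The disputed region needs a combined elevation, for which no frequency is given.

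**Conclusion.** The point holds as an inconsistency between current passages. Some severe combined elevations meet both the Section 6.3.1 stopping criterion and an Attachment 10 row that permits resumption, and the row contains no deferral. The existence of the overlap does not depend on the assumed Grade 2 cut-points. Its extent depends on those cut-points and on the undefined Hy's Law qualifier, and its effect on discontinuation counts or evaluability cannot be sized from the documents.

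The secondary point is narrower: patients with entry ALT below 3×ULN who reach ALT above 5×ULN with bilirubin above 1× and below 2×ULN are withheld without meeting a Section 8.1.4 trigger. Other surveillance continues. Reading the 3- and 4-week hold limits as a contradiction goes too far, since they measure different things. The matter should be corrected because it concerns a safety stopping rule, but it does not undermine the design.

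**What to change.** Reconcile Section 6.3.1, Section 8.1.4 and the Attachment 10 hepatobiliary row so that one combination of results leads to one instruction. State which passage governs where they overlap, and put that statement in the Attachment 10 row itself. Define what counts as a case confirmed by Hy's Law. Add a cross-reference between the Attachment 10 hold limit and the one in Section 7.2.1. The rule and the thresholds are for the sponsor's clinical team to choose; no view is offered here on which is right. The cost is protocol wording. The reconciliation itself calls for no added tests, since the chemistry panel already includes AST, ALT and bilirubin.
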